### 16.6. HANDLING OF MISSING DATA

The primary statistical analysis will be conducted using the observed data with standard imputations used when the 12 month DUS determination is missing but an earlier or later DUS

or angiogram are available in the ITT sample (see Primary Statistical Analysis in **Section 16.8** for more detail).

Additionally, a sensitivity analysis to the missing data in the intent-to-treat sample will be conducted. The sensitivity analysis will include a best case, worst case and tipping point analysis. The best case analysis will impute successes for the missing data. The worst case analysis will impute failures for missing data. The tipping point analysis starts with the best case analysis and continues until the worst case analysis is completed, by increasing the number of missing cases imputed as failures by one in each analysis. The goal of the tipping point analysis is to determine at what point the imputation of failures causes the statistical evaluation of the endpoint to lose statistical significance. If the worst case analysis maintains statistical significance, the tipping point analysis is not necessary.

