**Table 8 - Power for N=178 Subjects Varying the Proportion of Subjects Treated with DCB + Tack Meeting the ITT Definition with Data Available to Evaluate the Primary Efficacy Endpoint at 12 months**

Proportion of Subjects Meeting ITT Definition with Tack +		Performance Goal a	Assumed Patency at 12M for TOBA II			Power at N=178
DCB	Control PTA		DCB + Tack	Control PTA + Tack	Pooled	
30%	70%	49%	65%	65%	65%	99.1%
40%	60%	50%				98.0%
50%	50%	52%				92.4%
60%	40%	53%				90.0%

aThe performance goal, PG, is calculated as PG = proportion DCB + Tack\*59 + proportion control PTA + Tack\*44.

*Primary Statistical Analysis:* The primary statistical analysis will be conducted in subjects who meet the ITT definition and have data evaluable for the primary efficacy endpoint. Subjects with a missing DUS ultrasound at 12 months and a patent DUS ultrasound at a later visit with no intervening clinically driven TLR will be considered patent at 12 months. In the event an angiogram is available within the 12 month visit window, the angiographic core-lab determined stenosis using the 50% cutoff will be used instead of the DUS core-lab determined stenosis. The primary statistical method is a one-sample exact test comparing the proportion of subjects with

primary patency to the performance goal using a one-sided  $\alpha = 0.025$ . The exact two-sided 95% confidence interval for the proportion of subjects with primary patency will be calculated.

The primary patency proportion will be calculated such that the numerator is the number of subjects who are patent at 12 months with no clinically-driven TLR by the close of the 12 month visit window. The denominator is the total number of subjects with a core-lab adjudicated DUS ultrasound finding of either patent or not patent at 12 months, clinically-driven TLR prior to the close of the 12 month visit window, or missing 12 month DUS with a patent DUS finding at a subsequent visit with no intervening clinically driven TLR.

*Additional Analysis:* If pooling is not justified per the methods outlined in **Section 16.5**, the additional analyses specified in that section will be completed. If there is missing data for the ITT subjects, the sensitivity to missing data analysis outlined in **Section 16.6** will be completed. Additionally, the primary statistical analysis will be conducted in the per protocol sample.

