Duplex Ultrasound (DUS)	A form of medical ultrasonography that includes the following elements on the same screen (“duplex”) to facilitate interpretation 1) B-mode, pulsed Doppler display to visualize the structure within a vessel and 2) Color-Doppler display to visualize the blood flow and hemodynamics within a vessel.
Index Procedure	The interventional procedure during which treatment with the Study Device occurs.
Intent-to-treat (ITT) subjects	A subject is defined as an intent-to-treat (ITT) patient and officially enrolled in the study once the Tack Endovascular System is advanced through the introducer sheath.
Luminal Patency	Restenosis <50% as determined by angiography or duplex ultrasound.
Major Adverse Event (MAE)	Index limb amputation (above the ankle), Clinically-driven target lesion revascularization, or All-cause death
Myocardial Infarction (MI)	Q wave MI (QWMI): requires one of the following criteria: 
 
• Chest pain or other acute symptoms consistent with myocardial ischemia and new pathological Q waves in two or more contiguous ECG leads
 
• New pathologic Q waves in two or more contiguous ECG leads and elevation of cardiac enzymes above normal.
 

	
Non-Q Wave MI (NQWMI): defined as either: elevated CK = 2X the laboratory upper limit of normal with the presence of an elevated CK-MB (any amount above the laboratory upper limit of normal) in the absence of new pathological Q waves or elevated CK-MB = 3X the laboratory upper limit of normal in the absence of new pathological Q waves.

Peak Systolic Velocity Ratio (PSVR)	
A measurement (using Duplex Ultrasonography) of peak velocity of blood (cm/sec) within a lesion or stented vessel segment that is divided by the peak velocity of blood (cm/sec) proximal to the lesion of stented segment.

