Per-protocol (PP) subjects	
The per-protocol (PP) population is defined as ITT subjects with evaluable data that have met the definition for device success, excluding subjects with major protocol deviations such as:
 
 
▪ A major inclusion/exclusion criterion violation; or
 
▪ A major procedural deviation
 
 
The criteria for deviations meeting the classification of “major” will be defined before study endpoint data is available for statistical analysis. All major deviations will be adjudicated by an independent designee without visibility to study results.

Primary Efficacy Endpoint	
Primary patency defined as freedom from CEC adjudicated clinically-driven target lesion revascularization (CD-TLR) and freedom from core lab adjudicated duplex ultrasound derived binary restenosis at 12 months (defined as PSVR <math>\geq</math>2.5)

Primary Safety Endpoint	
Freedom from the occurrence of any new-onset major adverse event(s) (MAEs) defined as index limb amputation (above the ankle), CEC adjudicated clinically-driven target lesion revascularization (CD-TLR), or all-cause death at 30 days.

Procedure Start/End Time	
Start: The time of insertion of introducer sheath End: The time of withdrawal of last post-Tack PTA balloon catheter

Procedural Success	
Demonstrated vessel patency (<30% residual DS, by visual estimate) without the use of a bailout stent or the occurrence of MAE upon completion of the index procedure.

Renal Insufficiency	
An increase in serum creatinine of <math>\geq</math> 1.0 mg/dL over previous value requiring medical treatment but which does not require dialysis to resolve, or a serum creatinine level >2.5 mg/dL at baseline (subject should not be enrolled)

Restenosis	
Reoccurrence of narrowing or blockage or target lesion.

Rutherford Classification	Clinical scale identifying three grades of claudication and three grades of critical limb ischemia ranging from rest pain alone to minor and major tissue loss. (ACC/AHA PAD Practice Guidelines – Hirsch et al. 2005)
Class	Clinical Description
0	Asymptomatic
1	Mild claudication
2	Moderate claudication
3	Severe claudication
4	Ischemic rest pain
5	Minor tissue loss
6	Ulceration or gangrene

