
Target Lesion
	
Has a de novo or non-stented restenotic target lesion indicated for PTA treatment with a standard or FDA-approved Lutonix drug-coated balloon catheter that meets the following criteria below:
 
 
a. 70% to 99% stenosis with a total lesion length of <math>\geq 20</math>mm and <math>\leq 150</math>mm in length (by visual estimate) or;
 
b. 100% occluded with a total lesion length <math>\leq 100</math>mm (by visual estimate)
 
 
Notes:
 
A tandem lesion, defined as a lesion comprised of diseased and healthy segments, is eligible if the healthy segments are each not more than 30mm in length and all other criteria, including 3a and 3b above, are met
 
A combination lesion, defined as a continuous lesion with both non-occluded and 100% occluded segments, is eligible if the lesion can be treated as a single lesion and all other criteria, including 3a and 3b above, are met
 
 
c. A non-stented restenotic lesion must meet the following criteria: 
 
i. Meets criteria 3a and 3b
 
ii. No part of the target lesion has been previously treated with a drug-coated balloon
 
iii. No part of the target lesion has had more than 2 previous PTA failures
 
iv. <math>>90</math> days from most recent angioplasty treatment
 
 
 

Target Lesion Revascularization, Clinically-driven (CD-TLR)
	
Any re-intervention within the target lesion having angiographic evidence of <math>>50\%</math> diameter stenosis and the presence of symptoms associated with the target limb (defined as an increase in Rutherford Classification and a decrease in ABI <math>>0.15</math> from pre-discharge).

Target Lesion Revascularization (TLR)
	
A repeat revascularization procedure (percutaneous or surgical) of the original target lesion site.

Target Vessel
	
The superficial femoral artery (SFA) and/or proximal popliteal artery (above the knee), located <math>\geq 1</math> cm below the common femoral artery (CFA) bifurcation to the distal segment of the proximal popliteal (P1) artery at the superior end of the patella.

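### An index-limb amputee with no CD-TLR and no 12-month patency reading is handled as a missed scan, and scored a success in the best case; probably a small effect

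*Combined protocol and SAP*

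**What the plan says.** All references are to the combined protocol and SAP.

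- **Endpoint (Sections 6.1, 16.9 and 19).** "Primary patency defined as freedom from CEC adjudicated clinically-driven target lesion revascularization (CD-TLR) and freedom from core lab adjudicated duplex ultrasound derived binary restenosis", read at 12 months. There are two ways to fail.
- **CD-TLR (Section 19).** It begins "Any re-intervention within the target lesion having angiographic evidence of" more than 50% stenosis, and also needs symptoms. An amputation alone does not meet it.
- **Denominator (Section 16.9).** The first route in is a duplex reading: "The denominator is the total number of subjects with a core-lab adjudicated DUS ultrasound finding of either patent or not patent at 12 months". The second is "clinically-driven TLR prior to the close of the 12 month visit window", which is a failure. The third is "missing 12 month DUS with a patent DUS finding at a subsequent visit with no intervening clinically driven TLR", which is a success. If an angiogram is available in the 12-month window, "the angiographic core-lab determined stenosis using the 50% cutoff will be used instead of the DUS core-lab determined stenosis".
- **Missing data (Section 16.6).** "The best case analysis will impute successes for the missing data". The worst case imputes failures, and the tipping-point analysis moves from one to the other a subject at a time. No exception is made for amputation.
- **Where amputation counts.** The MAE definition in Section 19 is "Index limb amputation (above the ankle), Clinically-driven target lesion revascularization, or All-cause death". The primary safety test in Section 16.8 uses MAEs to 30 days only. After that, amputation is an observational endpoint (Section 6.2).

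**The concern.** The plan ranks above-ankle amputation of the index limb with death as a major adverse event, yet the efficacy analysis has no rule for it. Between day 31 and the close of the 12-month window, an amputation with no CD-TLR and no patency reading enters neither primary test. The subject is handled like someone who missed an appointment.

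The two are not alike. A missed appointment may have nothing to do with the artery, whereas an absent reading after limb loss may be a consequence of vessel failure. Dropping such subjects can favour the device in the observed-data analysis, which decides the trial. Scoring them as successes in the best case gives an upper bound that few readers would accept for a subject who has lost the limb.

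**Working it through.** **Inputs.** From Section 16.9: performance goal 53% (at 60% DCB), assumed patency 65%, one-sided alpha 0.025, exact one-sample test, 178 evaluable. From Section 16.3: 15% attrition, 210 enrolled. The share of subjects who are amputees without a reading is not in the documents, so a range is assumed below.

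**1. The plan's own figures.** The pass mark is the smallest r with P(X ≥ r | n, 0.53) ≤ 0.025. For n = 178, r = 108, the exact size is 0.0237 and power at 65% is 0.9004, matching the stated 90.0%. Enrolment is 178 / 0.85 = 209.4, rounded up to 210. These figures are not in dispute.

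**2. What happens to an amputee.**

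| Data before the window closes | Primary analysis | Best case | Worst case |
|---|---|---|---|
| Adjudicated CD-TLR | failure | failure | failure |
| 12-month DUS or in-window angiogram, not patent | failure | failure | failure |
| 12-month DUS or in-window angiogram, patent | success | success | success |
| None of these | dropped | success | failure |

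The point concerns the last row only. A later patent DUS could return such a subject as a success, but scheduled DUS ends at 12 months (Table 5). Section 16.6 also mentions an earlier DUS, but Section 16.9 gives no rule for using one. An amputee with a non-patent 6-month scan and no CD-TLR therefore has no stated handling.

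**3. Effect on the false-pass rate.** Suppose true patency is exactly 53% when these amputees count as failures. Dropping a share a of all subjects gives a tested rate of 0.53 / (1 − a) with n = 178 × (1 − a), rounded.

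| Dropped (assumed) | n | Tested rate | Pass mark | Exact size at 53% | P(pass) |
|---|---|---|---|---|---|
| 1 subject | 177 | 0.53 × 178/177 = 53.30% | 108 | 1.92% | 2.33% |
| 1% of subjects | 176 | 0.53/0.99 = 53.54% | 107 | 2.25% | 3.13% |
| 2% of subjects | 174 | 0.53/0.98 = 54.08% | 106 | 2.14% | 4.09% |

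**4. Effect on an observed result.**

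- At the boundary: 108/178 gives p = 0.0237 (pass). With one amputee added as a failure, 108/179 gives p = 0.0289 (fail).
- At the planned rate: 116/178 = 65.2%. With 5 amputees added as failures, 116/183 gives p = 0.0029. With 14, 116/192 gives p = 0.0231 (pass). With 15, 116/193 gives p = 0.0280 (fail).

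**5. Effect in Section 16.6.** Take 210 enrolled, 32 missing (210 − 178) and 116 observed successes.

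- Best case: (116 + 32)/210 = 148/210 = 70.5%. If 5 of the 32 are amputees fixed as failures, it is 143/210 = 68.1%.
- Worst case: 116/210 = 55.2%, p = 0.28. It fails whether or not any missing subject is an amputee.

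**The case against.** The strongest case against has four parts.

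- **Most routes to failure are already covered.** A reader might infer that no amputation after day 30 can count against the device. The documents do not support that. CD-TLR before the window closes, a non-patent DUS and an in-window angiogram over the cutoff are all failures. The target vessel ends above the knee, so an amputation lower down can leave the segment scannable, and Section 12.8 asks for imaging at unscheduled target-limb visits where indicated. This stands, and it confines the point to the last row of the table.
- **The sensitivity analyses bracket the problem.** The worst case fails every missing subject. This stands in part: it bounds the effect but cannot isolate it, because at the planned rates it fails on ordinary attrition alone.
- **The false-pass figures change the estimand.** A reader might infer that the plan's test exceeds its type I error on its own endpoint. It does not. The 3.1% and 4.1% arise only if amputees are deemed failures, which the plan's endpoint does not say, and nothing in the documents shows that an amputee's target lesion was occluded. This stands.
- **The goal comes from Levant 2.** Section 16.9 says that trial used the same efficacy endpoint. Adding amputation to this trial's primary definition alone would test a stricter endpoint against a goal not built for it. This stands, and is why the fix leaves the primary endpoint alone.

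**Conclusion.** The gap is real but narrow. An index-limb amputee with no CD-TLR and no qualifying reading is dropped from the primary test and scored a success in the best case and at the start of the tipping-point sequence. The missing reading may be related to the outcome, and no planned analysis separates it from an ordinary missed scan.

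The effect is probably small. The documents give no amputation rate, and Section 7.5.3 excludes Rutherford 5 and 6 and planned amputation. The 1% and 2% are assumed shares of all subjects, and those subjects must also lack CD-TLR and imaging. With a single such subject the false-pass rate stays under 2.5%. The handling could decide a result at the pass mark, but not one near the planned 65% unless 15 or more such amputees were added to 116/178. Severity: minor.

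**What to change.** Leave the primary endpoint and primary test as they are, to keep the match with Levant 2. Add two statements before outcome data are seen.

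- **Section 16.9, additional analysis.** Repeat the primary exact test with every ITT subject who had an above-ankle index-limb amputation before the close of the 12-month window, and who has neither CD-TLR nor a patency reading under the section's rules, counted as not patent: in the denominator and not in the numerator. Report the number of such subjects.
- **Section 16.6.** State that these subjects are fixed as failures in the best-case and tipping-point analyses, so that only the other missing subjects vary.

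The cost is one extra analysis and slightly lower patency in it. Amputation is already an observational endpoint and a reportable MAE, so no new data are needed.

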#### **Table 5. Time and Events Schedule**

Assessment	Baseline 	Implant Procedure	Pre-Discharge	30-day (-2 days/+14 Days)	6 Month (±30 Days)	12 Month (± 30 Days)	24 Month (± 30 Days)	36 Month (± 30 Days)	Unscheduled 
Informed Consent	X 								
Medical History / Physical Exam	X								
Serum Creatinine	X								
PT/ INR 	X								
Urine pregnancy test if female 	X								
Ankle Brachial Index (ABI)	X		X 	X	X	X	X	X	X
Rutherford Classification	X			X	X	X	X	X	X
Pre-procedural Medications		X							
Angiogram		X							X 
Study Medications		X	X	X	X	X	X	X	X
Duplex Ultrasound (DUS) 				X	X	X			X 
X-ray of Implanted Tacks 						X 			X 
Adverse Event Assessment		X	X	X	X	X	X	X	X
Peripheral Artery Questionnaire (PAQ)	X			X	X	X	X	X	X
EQ-5D-3L	X			X	X	X	X	X	X
Walking Impairment Questionnaire (WIQ)	X			X	X	X	X	X	X

 Assessments may be done up to 30 days before the procedure, with the exception of a pregnancy test

 Consent to be obtained within 30 days prior to enrollment.

 PT/INR to be obtained only if subject is on chronic warfarin therapy.

 Negative urine pregnancy test within 7 days of the Index Procedure is required for women of childbearing potential.

 All scheduled DUS exams should be performed per the protocol established by the core lab. If a DUS is non-diagnostic (per the imaging protocol), the site should make every effort to obtain a repeat exam within the visit window.

 Assessment of Tack Integrity. All required and unscheduled X-ray exams should be performed in accordance with the core lab protocol.

 Unscheduled visit data should be captured for a target limb related adverse event or intervention to target limb. If intervention to the target limb occurs, the data for assessments performed prior to the interventional procedure should be recorded in the eCRF.

 Only required for subjects in whom at least one Tack was placed during the index procedure.

 If clinically indicated or per standard of care.

 Pre-discharge ABI may be assessed up to 72 hours post-index procedure.

NOTE: All imaging of the target limb acquired during scheduled and unscheduled visits (such as Angiogram, DUS or X-Ray) should be submitted to the respective core lab within 3 days of occurrence.

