### 11.1. REQUIRED ASSESSMENTS

Assessments required at pre-discharge include the following:

- Target limb resting ABI Measurement (within 72 hours post-index procedure)
- Adverse event occurrence
- Study medication assessment

All subjects receiving treatment with a Tack should be provided with the Tack Endovascular System Patient Implant Card (PIC). The PIC is designed for the patient to carry along with their insurance cards. This PIC is to be completed by the designated research personnel to include information pertaining to the Tack device(s) including the model, lot number and location of the implanted Tack(s) and the date of the index procedure. The card also provides manufacturing information and MRI Compatibility.

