#### 12.8. UNSCHEDULED VISITS

A subject who presents to the investigational site between scheduled study-required follow-up visits for a target limb related adverse event or intervention to target limb is considered to have an “unscheduled visit”. Every effort should be made to gather data from the same clinical assessments required at the 12 month follow-up visit, including angiographic (if Target limb revascularization occurs), DUS and X-ray imaging (if clinically indicated or per standard of care). At the very least, target limb resting ABI measurement and Rutherford Classification should be assessed prior to any intervention to the target limb. In any case, if a Target limb intervention occurs, all the data from any assessment (clinical or imaging) performed prior to the intervention should be recorded in the Unscheduled Visit eCRF.

In the event a subject receives an intervention on the target vessel and/or lesion, all associated media (angiographic, DUS and X-Ray) shall be performed in accordance with imaging protocols and should be provided to the respective core labs. If a subject presents for target limb intervention that does not involve the target vessel/lesion, but the imaging performed captures the target lesion and Tacked portion vessel, such imaging should be sent to the respective core lab.

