## 13. RISK/BENEFIT ASSESSMENT

### 13.1. RISKS

The use of the Tack Endovascular System in percutaneous transluminal balloon angioplasty (PTA) may result in anticipated potential risks or complications similar to other available endovascular implant devices (such as stents) used in PTA procedures. Such risks are included in the Tack Endovascular System Instructions for Use (IFU) and are listed below:

- Access failure or abrupt closure
- Allergic / anaphylactoid reaction to anticoagulant and/or antithrombotic therapy or contrast medium
- Allergic reaction to nitinol
- Amputation of lower extremity
- Anemia
- Angina / coronary ischemia / myocardial infarction
- Arrhythmia
- Arterial occlusion / (re) stenosis / dissection / thrombus
- Arterial spasm
- Arteriovenous fistula
- Blue toe syndrome
- Claudication or rest pain, worsened
- Death
- Disseminated intravascular coagulation
- Edema, peripheral
- Embolism
- Emergent repeat hospital intervention
- Fever
- Gangrene
- Gastrointestinal bleed from anticoagulation / antiplatelet medication
- Hematoma / hemorrhage
- Hypotension / hypertension
- Inadvertent venipuncture
- Infection / abscess at insertion site
- Inflammation
- Multi-organ failure
- Pain
- Pseudoaneurysm
- Renal insufficiency or failure
- Respiratory distress or failure
- Septicemia / bacteremia (sepsis)
- Tack implant embolization
- Tack implant migration (device moves over time)
- Tack implant occlusion / restenosis

- Tissue necrosis
- Trauma to adjacent structures
- Stroke / TIA (hemorrhagic / embolic)
- Vascular complications which may require surgical repair

These risks are present in any endovascular treatment procedure for which the study subjects would be indicated because of their disease and will be reviewed with all subjects during the informed consent process.

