#### 16.8. PRIMARY SAFETY OBJECTIVE

Subjects Included the Analysis: Subjects who meet the ITT definition as specified in **Section 16.2 and 10.3.1**.

Endpoint: Freedom from the occurrence of any new-onset major adverse event(s) (MAEs) defined as index limb amputation (above the ankle), CEC adjudicated clinically-driven target lesion revascularization (CD-TLR), or all-cause death at 30 days as specified in **Section 6.1**.

Hypothesis and Performance Goal: The VIVA performance goal of 88% will be used as the performance goal for this endpoint.

H0: Freedom from MAE (pMAE) is less than or equal to 88% at 30 days, pMAE ≤ 88%

H1: Freedom from MAE is greater than 88% at 30 days, pMAE > 88%

Sample Size Rationale: Using PASS 2012, a one-sample Exact Test, power = 90%, one-sided Type I error controlled at 5.0%, a performance goal of 88% and an assumed freedom from MAE at 30 days in Group 1 of 95%, 138 subjects with 30 days of follow-up and/or an MAE prior to 30 days are required for the analysis.

---

**Primary Statistical Analysis:** The primary statistical analysis will be conducted in subjects who meet the ITT definition and have observed data for the primary safety endpoint. The primary statistical method is a one-sample exact test comparing the proportion of subjects free from a MAE to the performance goal using a one-sided  $\alpha = 0.05$ . The exact one-sided 95% confidence interval for the proportion of subjects free from MAE will be calculated.

The freedom from MAE proportion will be calculated such that the numerator is the number of subjects in whom a MAE did not occur within 30 days of the index procedure. The denominator is the number of subjects with 30 days of follow-up plus the number of subjects with an MAE prior to 30 days who exited the study early, if any.

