### 18.7.2. CLINICAL EVENTS COMMITTEE (CEC)

An independent Clinical Events Committee consisting of a team of clinical experts with experience in the conduct of clinical trials shall be formed to review clinical events reported by the investigators, or at the request of the Sponsor to determine if they meet the pre-specified endpoint definitions. The CEC may also be called upon to review relevant Serious Adverse Events to make an assessment of relationship to study device and/or study procedure. The CEC's determination of whether a clinical event meets the study defined endpoint will be considered the primary determination for the purpose of reporting study results with the exception of endpoints derived from Core Laboratory analysis.

Operational provisions shall be established to minimize potential bias (i.e., the physicians serving on the CEC shall be blinded to the clinical site to the extent possible during adverse event review and adjudication). The methodology for performing these responsibilities will be outlined in the CEC Charter. The CEC will define the minimum required information necessary to facilitate their review of an event. This may include information from original source documentation and imaging media.

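### The CD-TLR and CD-TVR definitions require an ABI fall from the pre-discharge value and give no rule for when that reference does not yet exist or either ABI is missing or unreliable

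*Combined protocol and SAP*

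**What the plan says.** Section 19 builds CD-TLR from conditions that must all hold. It starts from "Any re-intervention within the target lesion having angiographic evidence of" more than 50% diameter stenosis, and adds "and the presence of symptoms associated with the target limb (defined as an increase in Rutherford Classification and a decrease in ABI" of more than 0.15 from pre-discharge. CD-TVR carries the same symptom clause. Pre-discharge is the only ABI reference named.

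Timing of the reference: Section 11.1 lists "Target limb resting ABI Measurement (within 72 hours post-index procedure", and a footnote to Table 5 repeats that "Pre-discharge ABI may be assessed up to 72 hours post-index procedure".

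ABI at the event: Section 12.8 says "At the very least, target limb resting ABI measurement and Rutherford Classification should be assessed prior to any intervention to the target limb". It does not say what follows if this is not done.

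Adjudication: Section 18.7.2 asks the CEC to review reported events "to determine if they meet the pre-specified endpoint definitions". The CEC sets the minimum information it needs, and its methods are left to a charter that is not among the documents.

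Use: CD-TLR is the only re-intervention term in either primary endpoint. For safety, Section 16.8 sets a 30-day horizon and states "The freedom from MAE proportion will be calculated such that the numerator is the number of subjects in whom a MAE did not occur". For efficacy, Section 16.9 requires patency at 12 months and no clinically-driven TLR by the close of that visit window.

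**The concern.** Because the ABI fall is mandatory, the definition needs two usable values: one from before discharge and one at the event. Two situations break this.

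1. **Re-intervention before the reference is taken.** Section 13.1 lists "Access failure or abrupt closure" and occlusion of the implant among the risks. If the segment fails and is re-treated before the pre-discharge ABI, there is nothing to fall from. An ABI taken afterwards reflects the re-treated vessel.
2. **Either ABI missing, or unreliable because the ankle arteries are non-compressible.** The fall then cannot be shown, or cannot be shown reliably. No eligibility criterion concerns ABI or compressibility.

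In both, an unavailable measurement would have the same effect as an absent event. Early loss of the treated segment is what a 30-day safety endpoint should register, and the misclassification runs one way, towards the device.

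**Working it through.** **The plan's own figures.** One-sample exact binomial test: find the smallest r with P(X ≥ r | goal) ≤ α.

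- Safety (Section 16.8: goal 88%, assumed rate 95%, one-sided α 0.05, power 90%). The smallest N reaching 90% power is 138. Passing needs at least 128 of 138 event-free (at most 10 MAEs), with exact α 0.0493 and power 91.4%. The stated 138 reproduces.
- Efficacy (Section 16.9: goal 53%, assumed rate 65%, one-sided α 0.025, power 90%). The smallest N is 178. Passing needs at least 108 patent, with exact α 0.0237 and power 90.0%. The stated 178 reproduces.
- Enrolment (Section 16.3): 178 / 0.85 = 209.4, hence 210.

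The sample size is not in question. The issue is which events are counted.

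**How an affected subject is scored, taking the text literally.**

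- Safety: the subject is re-treated on day 1, before the pre-discharge ABI, and followed to day 30. No CD-TLR is established, so the subject enters both numerator and denominator as event-free. The outcome is observed, not missing, so the best-case, worst-case and tipping-point analyses of Section 16.6 do not reach it.
- Efficacy: the subject is re-treated at, say, month 4 without a usable pair of ABIs. With no CD-TLR recorded, the 12-month image decides, and that image shows the re-treated vessel.

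**Size for safety (illustration).** Assume all 210 enrolled subjects have 30-day data. Passing needs at least 193 event-free (at most 17 MAEs). Let the true rate equal the 88% goal, and let m true events go uncounted.

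- Exactly m uncounted: P(X ≥ 193 − m), with X ~ Bin(210, 0.88).
- m uncounted on average: P(X ≥ 193), with X ~ Bin(210, 0.88 + m/210).

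| m | Exactly m | m on average |
|---|---|---|
| 0 | 4.6% | 4.6% |
| 1 | 7.3% | 6.9% |
| 2 | 11.0% | 10.1% |
| 3 | 15.9% | 14.5% |

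At N = 138 the same calculation goes from 4.9% to 8.7% with exactly one uncounted event (8.1% if one on average).

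**Size for efficacy (illustration).** At N = 178 and a true rate of 53%, one uncounted failure moves the pass probability from 2.4% to 3.3%. This applies only if that subject's re-treated vessel is also patent on the 12-month image.

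The documents give no value for m. The tables show sensitivity, not an expected effect.

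**The case against.** The strongest reply has four parts.

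- **Silence is not a rule.** No section says that an event with an unobtainable ABI is to be scored as no event. An independent CEC makes the determination, decides what information it needs, and may use source records and imaging. Its charter may cover the case. This stands as a limit on what can be asserted. It does not close the gap: Section 18.7.2 ties the CEC to the pre-specified definitions and gives it no stated power to set a condition aside.
- **Safeguards exist.** Section 11.1 requires the pre-discharge ABI, and Section 12.8 asks for an ABI before any target-limb intervention. These reduce missing values at the event. They cannot supply a reference that was not yet taken.
- **Other routes to failure remain.** A reader might infer that these re-interventions can never count as a primary event. The documents do not support that. The subject can still fail safety by death or amputation, and patency by 12-month core-lab ultrasound or an in-window angiogram. A non-compressible limb may still give a number, so a fall above 0.15 is unreliable rather than impossible.
- **Waiving ABI replaces an objective criterion with judgement in a non-blinded single-arm study.** This is a fair cost, and it is why the fix includes an analysis that needs no judgement.

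Two further inferences should be resisted. The calcification allowed by the eligibility criteria concerns the femoropopliteal target lesion, and the documents do not link it to ankle-artery compressibility. A loss of patency in percentage points also cannot be estimated: it would need assumed rates of unusable ABI and of symptomatic TLR, and every re-treated lesion would have to be patent on its 12-month image.

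**Conclusion.** The point holds in limited form. As worded, a symptomatic target-lesion re-intervention with more than 50% stenosis but no usable pair of ABIs does not meet CD-TLR. Unless another component fails, it is an observed success at 30 days and may be patent at 12 months. The direction is certain: any such error favours the device. The size is not known. At the performance goal, a single uncounted event is enough to take either test above its nominal level: safety from 4.6% to about 7% at N = 210, and efficacy from 2.4% to 3.3% at N = 178. These figures rest on an assumed count, complete 30-day data for safety and, for efficacy, a patent 12-month image. The pre-reference window is short, so the number may be zero. The case for acting is that a rule deciding both primary endpoints belongs in the definition, not in adjudication after the fact.

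**What to change.** Add to the CD-TLR and CD-TVR definitions, and mirror in the CEC charter:

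- If a re-intervention takes place after the index procedure is complete and before the pre-discharge ABI, or if the pre-discharge or event ABI is absent or non-compressible, the ABI condition does not apply. The event is clinically driven if there is more than 50% diameter stenosis and the CEC confirms target-limb symptoms.
- An ABI taken after a re-intervention is not used as the pre-discharge reference.

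Add to Sections 16.8 and 16.9 a sensitivity analysis of each primary endpoint that counts any TLR as a failure. TLR regardless of symptoms is already an observational endpoint (Section 6.2).

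Cost: wording in the definitions, the charter and the analysis plan, with no new visits or assessments and no change in sample size. There would be slightly more reliance on CEC judgement, and the event count may be less favourable to the device.
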